**2.2 Secondary Objectives**

Our secondary objectives are to optimize the integration of commercially available and in-development software that are needed to develop a Scan-Plan-Treat STAT RT workflow. Specifically, we plan to:

- 2.2.1** Optimize CT-detector-based exit dose measurement algorithms for quality assurance and compare them to traditional phantom quality assurance methods.
- 2.2.2** Optimize rigid and deformable co-registration of pre-contoured diagnostic image sets to MVCT simulation scans and compare the accuracy to the conventional method in which the same pre-contoured diagnostic image sets are co-registered to kilovoltage CT (kVCT) simulation images and then kVCT simulation is co-registered to the MVCT scan.
- 2.2.3** Validate an in-house infrared tracking system and monitor patient motion during treatment for all patients treated a ECCCC.

**2.3 Exploratory Objectives**

Not applicable.

## **3.0 PATIENT ELIGIBILITY**

### **3.1 Inclusion Criteria**

- 3.1.1** Patient has a biopsy proven diagnosis of cancer. The osseous metastatic lesions do not need to be biopsied.
- 3.1.2** Patients with multiple myeloma are eligible for the study.
- 3.1.3** Patient has 1-3 major painful osseous metastases (target lesions) from any primary cancer or unknown primary cancer.
- 3.1.4** Long bone target lesions must have a Mirels fracture score of  $\leq 7$  (See Appendix G).
- 3.1.5** Radiation oncologist determines that the patient is medically able to undergo palliative radiation therapy.
- 3.1.6** Patient has target lesions that are radiographically consistent with metastatic disease on CT, MR, or PET CT obtained within 8 weeks of treatment.
- 3.1.7** Persistent distinguishable pain associated with target sites to be treated.
- 3.1.8** Patient average BPI pain score for last 72 hours at specified location is  $\geq 3$  (0-10 scale)
- 3.1.9** Patients may have additional non-painful or minimally painful osseous metastases (if patient has pain from additional sites, the pain from the additional sites must be evaluated as being less intense by at least 2 points on the BPI compared to the site(s) treated)
- 3.1.10** The patient may have previously been treated with external beam radiation therapy to other body sites, but not to the target sites.
- 3.1.11** The patient may have previously or currently be undergoing chemotherapy or bisphosphonate therapy.

- 3.1.12** The patient will be able to understand English (or a medical interpreter for their native language must be available for all study visits).
- 3.1.13** 18 years of age or older.
- 3.1.14** Life expectancy > 12 weeks.
- 3.1.15** Able and willing to answer simple survey questionnaires.
- 3.1.16** Able and willing to keep a logbook of analgesic use (with or without assistance)
- 3.1.17** Willing to return to clinic at 4 weeks, 12 weeks, 6 months, and 12 months after treatment.
- 3.1.18** Signed study-specific informed consent form.
- 3.1.19** Women of childbearing potential and men must agree to use adequate contraception (hormonal or barrier method of birth control) prior to study entry and for the duration of study participation. Should a woman become pregnant or suspect she is pregnant while participating in this study, she should inform her treating physician immediately.
- 3.1.20** The radiation oncologist plans to treat the patient's target lesions with a total of 2-5 fractions of high dose palliative radiation therapy consisting of 5-10 Gy per fraction with a minimum biologic effective dose (BED) of 25 Gy.

## **3.2 Exclusion Criteria**

- 3.2.1** Inability to lie flat on table for treatment
- 3.2.2** Patient with  $\leq$  12 weeks life expectancy
- 3.2.3** Systemic therapeutic radionuclide delivery within 30 days prior to treatment
- 3.2.4** Epidural compression of spinal cord or cauda equine
- 3.2.5** Long bone target lesions must have a Mirels fracture score of  $\leq$  7
- 3.2.6** Spinal canal compromise > 25%
- 3.2.7** Unstable spine requiring surgical stabilization

**3.2.8** Target lesions have previously been treated with external beam radiation.

**3.2.9** PTV located within 5mm of spinal cord or cauda equina.

**3.2.10** A serious uncontrolled medical disorder that, in the opinion of the Investigator, would impair the ability of the patient to receive protocol therapy.

**3.2.11** Pregnant and breastfeeding women are excluded from this study.

## **4.0 TREATMENT PLAN**

### **4.1 Schema**

|                                  | Tx                | Follow-Up         |                          |                          |                          |                          |                          |
|----------------------------------|--------------------------|--------------------------|--------------------------|--------------------------|--------------------------|--------------------------|--------------------------|
| Helical
TomoTherapy*: |                          |                          |                          |                          |                          |                          |                          |
| Assessments†:             |  |
| Week:                     | 0                 | 1                 | 4                 | 8                 | 12                | 26                | 52                |

\*1-5 helical TomoTherapy radiation treatments over 1-2 weeks

† Physical Exam (PE) and/or surveys

Treatment-related toxicity will be captured during treatment PEs and followup PEs.

- This is an investigator-initiated, prospective, non-randomized, multi-centered pilot phase II trial. The clinical trial will be open to accrual at UVA and CRH only.
- We anticipate that it will take approximately 24 months to accrue 30 patients to this pilot study, and each patient will plan to undergo 1 year follow-up.

### **4.2 Treatment Dosage and Administration: Radiation Therapy**

- Approved and consented patients will receive radiotherapy using the STAT RT workflow.
- The patients will receive Helical TomoTherapy using the Hi Art system (TomoTherapy Inc).
- Patients will receive a total of 2-5 fractions of high dose palliative radiation therapy consisting of 5-10 Gy per fraction with a minimum biologic effective dose (BED) of 25 Gy.

- **Dose specifications:** The planning target volume (PTV) will be prescribed a minimum BED of 25 Gy. The maximum dose prescribed will be a BED of 72 Gy.
- **Variations of dose prescription:** There is a wide acceptable range of doses delivered to bone metastases in the palliative setting. The appropriate dose will be determined by tumor histology (whether the tumor is radiosensitive or radioresistant) and location of critical structures (to prevent radiation-induced toxicity to adjacent organs at risk). Dose prescription will be at the discretion of the treating radiation oncologist, however will have to be at least a BED= 25 Gy.
  - **Beam Energy** 6 MV (TomoTherapy only has one beam energy)
  - **Beam Shaping** All treatments will be delivered with conformal delivery with multi-leaf collimator beam modulation.
- **Localization, Simulation and Immobilization:** All patients will undergo non-contrast enhanced kVCT simulations with standard immobilization devices: aquaplast masks for head, neck, upper thoracic PTVs, Vac-Lok cushions or custom headrests, body-fix immobilization system for spinal tumors are all permissible. Diagnostic contrast enhanced CT scans, PET CT scans, or MRIs from the patient's PACS chart will be used to guide target and OAR contouring. The diagnostic images will be rigidly (MRI, contrast enhanced CT, PET CT) or deformably (contrast enhanced CT, PET CT) co-registered to the kVCT simulation in Velocity. Following contour transfer to the kVCT simulation image set, the images will be reviewed and approved by a physician and then transferred to the TomoTherapy treatment planning station.
- An experimental contouring plan will be created to compare to the conventional treatment plan but will not be used in treatment planning. We will experimentally co-register the contoured diagnostic images directly to the MVCT scan and generate the PTV and OAR contours using only the MVCT scan without the kVCT intermediate. Contours generated by both methods will then be compared.
- **Treatment planning/Target Volumes:** Dose will be prescribed to a PTV which will be a gross target volume (GTV) expanded by 0-10 mm depending on critical adjacent structures.
- **Treatment Planning:** TomoHelical (rotational beam delivery) and TomoDirect (fixed beam delivery) techniques in either the IMRT and 3D planning modes are permissible.

- **Critical Structures**

The following are dose limitations to critical structures. These are accepted dose limitations that have been used in multiple clinical trials of radiotherapy (20, 60).

**Table 2: Critical Structures Dose Constraints**

| Organ                            | Volume               | Total Dose      |
|----------------------------------|----------------------|-----------------|
| Spinal cord                      | Any point            | 18 Gy maximum   |
| Esophagus                        | Any point            | 27 Gy maximum   |
| Ipsilateral brachial plexus      | Any point            | 24 Gy maximum   |
| Heart                            | Any point            | 30 Gy maximum   |
| Trachea and ipsilateral bronchus | Any point            | 30 Gy maximum   |
| Right and left lung              | <10% of volume       | 20Gy or greater |
| Liver                            | >700 cc normal liver | <15 Gy          |
| Single kidney                    | > 66% of volume      | <15 Gy          |
| Total Kidney Volume (L+R)        | < 35% of volume      | ≤15 Gy          |
| Stomach                          | Any point            | 30 Gy maximum   |
| Bowel                            | Any point            | 30 Gy maximum   |

- **Documentation requirements:** We will provide a dosimetry form that specifies the dosemetric criteria for the PTVs and OARs have been met for each study subject. This will ensure dosimetric compliance with PTV and OAR specifications. The treating radiation oncologist must sign this form for the study to continue.
- **RT Quality Assurance:** Standard quality assurance will be performed with all treatment plans. This involves the placement of a phantom with an array of radiation detecting ion chambers called OmniPro Matrixx on the couch of the TomoTherapy unit. The planned treatment is then delivered to theMatrixx phantom, and the ion chamber array ensures that the correct point dose and geometry is delivered. This ensures that the patient will get the dose as it was planned. Then, while the phantom and then the patient are irradiated, the fluence of the radiation exiting the patient will be measured by the CT detector. The exit dose verification software will then back-project this data collected by the CT detector onto the planning CT scan for volumetric or 3D dose reconstruction. This calculated 3D doses delivered will then be compared to the measured dose recorded by the phantom and also compared to the planned dose.

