Most significant adverse events in spinal SBRT have occurred with treatments that used extremely high-doses (>20 Gy) in a single fraction. Gomez et al reported odynophagia and dysphagia in 1 patient who had received 22Gy to the esophagus in a single dose, and another patient developed an esophageal ulcer and necrosis after receiving 24Gy to his esophagus in one fraction (34). Another patient developed bronchial stenosis after receiving 11Gy to a bronchus. In another study with similarly high dose fractionation schedules, 39% of patients treated with 18 to 24 Gy in a single dose developed new or progressive vertebral fractures (35). However, their patient selection did not utilize a scoring system to identify patients at high risk for pathologic fracture, such as the Mirels scoring system (36). In contrast, Gagnon et al, using mean doses of 26 Gy in 3 fractions in 200 patients, only had 2 patients (1%) develop vertebral fractures (31). Sahgal et al reported 5 cases of radiation myelopathy and concluded that for single fraction SBRT, up to 10Gy to a maximum point to the thecal sac is safe (37). Dose distributions that cause such severe toxicities described above will not be used in this study. Our study will use doses similar to those used by Gagnon for his SBRT studies that reported remarkably low toxicities. Additionally, to minimize the number of patients who develop new or progressive fractures, we will use the Mirels scoring system to identify patients at high risk of fracture and exclude them from the study (36).

[figure not shown]

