**Figure 1: Conventional Technique**

**Figure 2: Conformal Technique**

#### 1.3.4 Relative Biologic Effective Dose: a method to compare different dose fractionation schedules

Based on the linear-quadratic equation, one can calculate the biologic effective dose (BED) to compare dose delivery of different fractionation schedules using the equation:  $BED = nd [1+d/(\alpha/\beta)]$ , where  $n$  = number of fractions and  $d$  = dose per fraction. As seen in **Table 1**, when compared with conventional fractionation schedules for palliative osseous metastases, such as 30Gy in 10 fractions or 20Gy in 5 fractions, high dose per fraction regimens deliver very similar BED to early responding tissues and slightly higher BED to late responding tissues. Our study will deliver a minimum BED of 25 Gy to each treatment target. We anticipate that most patients on this trial will receive 2-3 treatments with 8 Gy delivered per treatment, however, the dose per treatment, number of treatments, and total dose will depend on patient-specific factors including tumor histology, tumor location and proximity to critical OARs, and tumor size. Relative BED provides a method to compare different dose fractionation schedules that can be used to correlate the treatment with patient outcomes.

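### Table 2 sets one total-dose limit per organ for courses of 2 to 5 fractions, so the same limit allows very different late-tissue doses, most clearly for the spinal cord

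*Combined protocol and SAP*

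**What the plan says.** Section 4.2 fixes the range of courses: "Patients will receive a total of 2-5 fractions of high dose palliative radiation therapy consisting of 5-10 Gy per fraction". It bounds the target dose in BED, with a minimum of 25 Gy and a cap: "The maximum dose prescribed will be a BED of 72 Gy". Section 1.3.4 gives the formula, says that with it "one can calculate the biologic effective dose (BED) to compare dose delivery of different fractionation schedules", and names the usual schedules: "We anticipate that most patients on this trial will receive 2-3 treatments with 8 Gy delivered per treatment".

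The normal-tissue limits in Table 2 are stated differently. Its columns are organ, volume and total dose, with no number of fractions and no BED. The any-point limits are 18 Gy for spinal cord, 24 Gy for brachial plexus, 27 Gy for esophagus, and 30 Gy for heart, trachea/bronchus (the row labelled "Trachea and ipsilateral bronchus"), stomach and bowel. Section 4.2 attributes the limits to earlier trials without saying what fractionation they were set for. The treating radiation oncologist must sign a dosimetry form confirming that the criteria are met.

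Section 1.3.2 reviews toxicity. It reports a review of myelopathy cases concluding that "for single fraction SBRT, up to 10Gy to a maximum point to the thecal sac is safe". It also reports one airway event: "Another patient developed bronchial stenosis after receiving 11Gy to a bronchus". It then undertakes: "Dose distributions that cause such severe toxicities described above will not be used in this study".

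The footnote to the schema in section 4.1 mentions 1-5 treatments. I take 2-5 as governing, because sections 3.1.20, 4.2 and 4.6 all say so.

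**The concern.** A limit in total Gy has a fixed biological meaning only when the number of fractions is fixed. Here that number ranges from 2 to 5, and the same total given in fewer, larger fractions is a higher late-tissue BED. A fraction-blind limit is therefore most permissive in the shortest courses. The protocol uses BED to bound the target dose but not to protect the organs beside it.

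At stake is what the signed form certifies. If a row was set for one fractionation and is checked against another, a signature shows that the number was met, not that the intended protection was given. Cord and bronchial injuries are the severe events that section 1.3.2 says the study will avoid. The toxicity holds in section 4.3 act during a course of at most 21 days, while section 1.5 defines late toxicity as arising 3 months or more after treatment. The dose limit is therefore the main control on late injury.

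**Working it through.** **Inputs.** Formula from section 1.3.4: BED = nd[1 + d/(alpha/beta)]. With total D = nd this is D[1 + (D/n)/(alpha/beta)]. Alpha/beta is 3 for late and 10 for early tissue, from Table 1. Table 2 states none, so using 3 for its organs is my assumption. Limits are from Table 2, schedules from sections 1.3.4 and 4.2, toxicity doses from section 1.3.2.

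**Reproducing Table 1.** The formula gives 39.0, 28.0 and 43.2 at alpha/beta 10, and 60.0, 46.7 and 88.0 at alpha/beta 3. The table prints 39, 28, 43, 60, 47 and 88, so all six agree.

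**Cord limit of 18 Gy, alpha/beta 3.**

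| Course | Working | BED | Ratio to single 10 Gy |
|---|---|---|---|
| 2 fractions | 18(1 + 9/3) | 72.0 | 1.66 |
| 3 fractions | 18(1 + 6/3) | 54.0 | 1.25 |
| 4 fractions | 18(1 + 4.5/3) | 45.0 | 1.04 |
| 5 fractions | 18(1 + 3.6/3) | 39.6 | 0.91 |
| Single 10 Gy | 10(1 + 10/3) | 43.3 | 1 |

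The range is 72.0/39.6 = 1.8-fold. At alpha/beta 2 the four values are 99, 72, 58.5 and 50.4 against 60, and the ordering is the same. At 2 x 8 = 16 Gy the 18 Gy limit is 112.5% of the prescription, so a cord point at full prescription (BED 58.7) would pass.

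**Which limits bind at the anticipated schedules.**

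| Structure | Limit (Gy) | % of 16 Gy | % of 24 Gy |
|---|---|---|---|
| Cord | 18 | 112.5 | 75 |
| Brachial plexus | 24 | 150 | 100 |
| Esophagus | 27 | 169 | 112.5 |
| Heart, trachea/bronchus, stomach, bowel | 30 | 187.5 | 125 |

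The last two rows cannot be reached at either schedule unless a point receives more than the prescription.

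**Bronchus, alpha/beta 3.** A single 11 Gy gives 11(1 + 11/3) = 51.3. Section 1.3.2 gives no fraction number for that dose. One fraction is assumed, and that choice gives 11 Gy its highest BED. Full 2 x 8 Gy gives 16(1 + 8/3) = 58.7, a ratio of 1.14. Full 3 x 8 Gy gives 24(1 + 8/3) = 88.0, a ratio of 1.71. Both pass the 30 Gy limit. At alpha/beta 10 the figures are 23.1, 28.8 and 43.2, in the same order.

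**Equal-BED cord limits.** Set D[1 + D/(3n)] = B and solve: D = [-3n + sqrt(9n² + 12nB)]/2. If 18 Gy is a 3-fraction value, B = 54 and for n = 2, D = [-6 + sqrt(36 + 1296)]/2 = 15.2. The protocol does not give the source fractionation, so the range is:

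| 18 Gy assumed set for | B | 2 fr | 3 fr | 4 fr | 5 fr |
|---|---|---|---|---|---|
| 2 fractions | 72 | 18 | 21.3 | 24 | 26.2 |
| 3 fractions | 54 | 15.2 | 18 | 20.2 | 21.9 |
| 5 fractions | 39.6 | 12.7 | 14.9 | 16.6 | 18 |

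**The case against.** Four objections deserve weight.

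First, a limit that does not bind at a low prescription is not thereby defective. If the esophagus and 30 Gy rows are 3-fraction values, their BED at alpha/beta 3 is 27(1 + 9/3) = 108 and 30(1 + 10/3) = 130. Full 2 x 8 or 3 x 8 Gy, at 59 and 88, ought to pass. The limits can also bind for hot spots, for overlapping dose from adjacent targets, and in longer courses such as 5 x 8 = 40 Gy. This stands. A reader might infer that these rows give no protection, but the documents do not support that without the source fractionation.

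Second, the bronchus event is one case with no denominator and an assumed single fraction. A reader might set 30 Gy against 11 Gy and conclude that Table 2 permits a dose known to be harmful. That compares totals across fractionations, and one case does not fix a tolerance. At 2 x 8 Gy the excess is only 1.14-fold. The undertaking in section 1.3.2 names no bronchus figure, and the same section likens the study's doses to a 200-patient series with a mean of 26 Gy in 3 fractions and few toxicities, a BED of 26(1 + 8.67/3) = 101. What remains is a tension between a general promise and the table.

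Third, section 3.2 excludes targets within 5 mm of the cord or cauda equina, epidural compression, and canal compromise above 25%. These exclusions lower the chance that the cord nears its limit. They do not make the limit right for every course.

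Fourth, physician discretion over dose, margins adapted to nearby structures, toxicity holds and the stopping rule in section 7.1 all give some protection. None is a fraction-specific limit that the form can check.

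**Conclusion.** The concern holds as a gap in specification. Nothing in the protocol makes Table 2 depend on the number of fractions, and by the protocol's own formula the cord row spans a 1.8-fold range of late-tissue BED. In 2 fractions it allows 1.66 times the BED of the single dose cited as safe. This rests on alpha/beta 3 for the cord, and on comparing a cord limit with a statement about the thecal sac, which is not the same structure. Whether 18 Gy is too high in 2 fractions or needlessly strict in 5 depends on what it was set for.

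For the five structures limited at 27 or 30 Gy, the finding is only that the protocol does not say whether non-binding limits are intended at 16-24 Gy. For the bronchus, it is an inconsistency to reconcile. Section 1.3.4 presents BED as a way to compare schedules. It does not say that total doses cannot be compared, and the point does not need it to.

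This should be fixed, because the stated rule permits the most late-tissue dose in the shortest courses. It is not a must-fix matter: no endpoint analysis depends on it, and eligibility already limits cord exposure.

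**What to change.** State the fractionation for which each Table 2 limit was derived. Then give the limits in columns for 2, 3, 4 and 5 fractions, or as BED with a stated alpha/beta per organ. As an illustration only, if 18 Gy to the cord is a 3-fraction value, the equal-BED limits at alpha/beta 3 are about 15.2, 18, 20.2 and 21.9 Gy. The values are for the sponsor to set from its sources.

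Have the dosimetry form record the planned number of fractions and check the matching column. Either tighten the trachea/bronchus row or qualify the undertaking in section 1.3.2 so that the two agree.

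The cost is an amendment to one table, one form and possibly one sentence. No new measurement is needed, because the check uses organ doses that the existing form already requires. The downside is that some 2-fraction plans may need re-optimisation.

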#### **b) Slow Workflow for Treatment Planning and Quality Assurance**

Conventional simulation and treatment planning is performed over a several day process prior to the first delivered treatment. The patient generally is first seen in consultation and scheduled for a CT simulation on a subsequent day. During the CT simulation the patient is placed in the position in which they will ultimately be treated on a linear accelerator (LINAC) or TomoTherapy unit, and immobilization and support devices are fabricated after which they undergo a CT scan in the treatment position. He or she must then wait, sometimes several days, for the contouring of the CT simulation images (a process by which the radiation oncologist specifies the planning target volume (PTV) of the tumor to be treated and the regional organs at risk (OARs) or adjacent tissues that may receive radiation resulting in toxicity). Following the contouring of the CT images, radiation treatment planning is performed, during which time medical dosimetrists and physicians determine the beam angles and treatment technique to deliver the prescribed dose to the PTV while attempting to minimize dose to OARs if possible. Again, for standard osseous metastatic disease palliative techniques

tend to be fairly simple. Following treatment planning, quality assurance calculations and/or measurements are performed by medical physicists before delivery of the first treatment to ensure accuracy of delivering the planned dose and ensure patient safety.

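### As transcribed, the total-kidney row of Table 2 does not state a valid organ limit; the dose sign appears reversed and should be checked against the source PDF and corrected

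*Combined protocol and SAP*

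**What the plan says.** Section 4.2 introduces Table 2 with "The following are dose limitations to critical structures". The table has eleven rows. Seven are point maxima. The other four are partial-volume criteria:

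- Lung: less than 10% of volume at "20Gy or greater".
- Liver: ">700 cc normal liver" at less than 15 Gy.
- Single kidney: more than 66% of volume at less than 15 Gy.
- Both kidneys together: "Total Kidney Volume (L+R) | < 35% of volume | ≤15 Gy".

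The table has an operational use. Under the documentation requirements that follow it, a dosimetry form records for each subject that the target and organ criteria were met, and "The treating radiation oncologist must sign this form for the study to continue". No other part of the document restates a kidney limit.

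**The concern.** A partial-volume organ limit can be written in two ways. It can cap the volume that receives a high dose (small volume, dose at or above a threshold), or it can require a volume to be spared (large volume, dose below a threshold). Either way the two signs point in opposite directions. In the total-kidney row both signs point downward. Taken as its neighbours are taken, the row caps the volume that is spared.

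What is at stake is a safety criterion that a physician signs. It matters for targets near the kidneys. Spinal targets are in scope, since section 4.2 says a "body-fix immobilization system for spinal tumors are all permissible", and some of these may lie at kidney level. The 15 Gy threshold is also relevant to the doses used: section 1.3.4 expects most patients to have two or three treatments of 8 Gy, which is 16 to 24 Gy in total. The Study Overview puts simulation, planning and first treatment on day 1, and section 4.1 has two sites accruing, so there is little time to resolve an unclear criterion case by case.

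**Working it through.** The plan gives no computed figure to reproduce, so this is a check of logic. All inputs are the four partial-volume rows of Table 2.

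**1. Direction of the signs**

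| Row | Volume sign | Dose sign | Directions |
|---|---|---|---|
| Lung | < 10% | ≥ 20 Gy | opposite |
| Liver | > 700 cc | < 15 Gy | opposite |
| Single kidney | > 66% | < 15 Gy | opposite |
| Total kidney | < 35% | ≤ 15 Gy | same |

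Three of four are opposite; one is not.

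**2. What the row requires.** Let f be the fraction of combined kidney volume receiving more than 15 Gy, ignoring volume at exactly 15 Gy.

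- As transcribed, read like its neighbours: (1 − f) < 0.35, so f > 0.65.
- Dose sign reversed (lung form): f < 0.35.
- Single-kidney row applied to each kidney: more than 66% of each is below 15 Gy, hence more than 66% of the two combined. So (1 − f) > 0.66, or f < 0.34.
- Volume sign reversed instead: (1 − f) > 0.35, so f < 0.65.

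| f | As transcribed | Dose sign reversed | Single-kidney row, each kidney | Volume sign reversed |
|---|---|---|---|---|
| 0 | fail | pass | pass | pass |
| 0.33 | fail | pass | pass | pass |
| 0.34 | fail | pass | fail | pass |
| 0.35 | fail | fail | fail | pass |
| 0.50 | fail | fail | fail | pass |
| 0.66 | pass | fail | fail | fail |
| 1 | pass | fail | fail | fail |

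As transcribed, the row fails a plan that spares the kidneys completely and passes one that puts both whole kidneys above 15 Gy.

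**3. Consistency with the single-kidney row.** If that row applies to each kidney, it needs f < 0.34, while the row as transcribed needs f > 0.65. No plan meets both. Volume at exactly 15 Gy does not rescue it: more than 66% strictly below 15 Gy implies more than 66% at or below 15 Gy, which cannot be under 35%.

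**4. Which sign to change.** Reversing the dose sign gives a 35% cap, within 35 − 34 = 1 percentage point of what the single-kidney row implies. Reversing the volume sign would allow almost 65% above 15 Gy, far from that row. The dose sign is the natural candidate.

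**5. Whether 15 Gy is in play.** Section 4.2 allows two to five fractions of 5 to 10 Gy, with BED from 25 to 72 Gy, where BED = nd[1 + d/(α/β)]. It does not state the α/β for those limits; Table 1 uses 10 and 3. With 10, permitted totals run from 14.5 Gy (2 × 7.25: 14.5 × 1.725 = 25.0) to 40 Gy (5 × 8: 40 × 1.8 = 72). With 3, they run from 10 Gy (2 × 5) to 26.2 Gy (5 × 5.24). Most of the permitted range lies above 15 Gy, so the threshold can matter when a kidney is close to the target.

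**The case against.** The strongest objection is that this may not be in the protocol at all. It turns on a single sign in a table converted from PDF by a program, and the inequality signs elsewhere in the converted text came through in a different form. A misread ≥ cannot be excluded. This stands, and it is why checking the source comes first.

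The second is that the dose column is an upper bound in ten of the eleven rows (seven maxima, two at < 15 Gy, and this one); only lung is written as a dose at or above a threshold. On that view the row is a ceiling, D35% ≤ 15 Gy, allowing at most 35% of combined volume above 15 Gy, and the only blemish is the < before 35%. That is very probably the intent. But the row lacks the wording of the maximum rows, and the < does not fit that notation, so the printed criterion still needs repair. The recommended form gives essentially the same limit.

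The third is that correction may change no acceptable plan. If *Single kidney* means each kidney, that row is already 1 percentage point tighter and the corrected total-kidney row never binds. If it means a solitary kidney, the contradiction in step 3 is not established, but the total-kidney row then becomes the only limit for patients with two kidneys. Either way the row should say what it means.

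A reader might infer more: that the plan directs planners to overdose kidneys, or that every signed form is affected. The documents do not support this. The table is introduced as dose limits, so a minimum kidney dose cannot be meant, and a radiation oncologist reviews each plan. Section 1.2.2 b) describes the contoured organs as "regional organs at risk (OARs) or adjacent tissues that may receive radiation", and section 4.2 sets dose with organ location in mind "to prevent radiation-induced toxicity to adjacent organs at risk", so kidneys may not be scored for distant targets. The dosimetry form was not available, so it is unknown whether it carries the same sign.

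**Conclusion.** As transcribed, the row is not a valid organ limit. Read like the other three partial-volume rows, it demands more than 65% of combined kidney volume above 15 Gy where the evident intent is at most about 35%. This conflicts with the table's stated purpose and, if the single-kidney row applies to each kidney, with that row as well.

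The conclusion assumes that the sign was read correctly from the PDF. The contradiction between the two kidney rows additionally assumes the each-kidney meaning. The practical safety risk is small, and nothing in the sample size, endpoints or analyses depends on it. The undefined term *Single kidney* is a missing detail, not part of the error. This is a low-priority correction, worth making because the table is an operative criterion that must be signed for each subject.

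**What to change.** 1. Check the dose sign in the total-kidney row against the source PDF. If it reads ≥ there, no change to the row is needed.
2. If it reads as transcribed, print the row as < 35% of volume at ≥ 15 Gy, or equivalently > 65% of volume at < 15 Gy.
3. Confirm that the dosimetry form carries the same criterion.
4. Optionally, state whether *Single kidney* means each kidney or a solitary kidney.

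The cost is one sign in one table row, a check of one form and, if wanted, one clarifying word.
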